Modified Vascularized Interpositional Periosteal Connective Tissue Graft Versus Xenogeneic Collagen Matrix For soft tissue Augmentation Around Implant in Esthetic Zone

(A Comparative Study)

Proposal

Presented By

[name]

21/11/2021

Introduction and Review

Immediate implant placement defined as the positioning of a dental implant immediately into fresh extraction socket after tooth extraction, it's a predictable and acceptable procedure for redressing missing teeth (Mazzotti, Stefanini et al. 2018).

The immediate implant placement in anterior maxilla represent one of the most challenging areas and require orchestrated steps and protocols to help achieving predictable and long term esthetic outcomes (**Dixon and Yassin 2020**).

Contrary to popular belief, it is now evident that labial bone contour cannot be maintained by placing implants in fresh extraction sockets. Dimensional changes, including the loss of labial soft tissues and mid buccal mucosal recessions, seem to be inevitable following immediate placement. Even when guided bone regeneration is simultaneously performed to correct peri-implant bone defects or to fill horizontal gaps between implants and socket walls, changes in soft tissue levels may still occur, particularly in the presence of thin gingival biotypes or inadequate width of keratinized tissues(Atieh and Alsabeeha 2020).

Peri-implant soft tissue has attracted great attention recently as it is hypothesized that a sufficient amount of keratinized mucosa may establish a stable epithelial seal around dental implants, which is beneficial for avoiding bacterial penetration (Huang, Liu et al. 2021).

Hence, thickening the soft tissue and increasing the amount of keratinized mucosa with autogenous soft tissue grafts (Chung, Rungcharassaeng et al. 2011) or tissue substitutes (Sanz, Lorenzo et al. 2009) were thought to reduce the risk of mucosal recession, maintain the stability of peri-implant mucosal level and compensate for peri-implant mucosal changes following immediate implant placement and restoration(IIPR) (Atieh and Alsabeeha 2020).

Most techniques of soft tissue augmentation procedure have the drawback of less gain in volume because of limited size of the graft that can be used. Large onlay grafts have chances of necrosis due to lack of sufficient blood supply (Cheng 2016).

In 2003, Sclar in his book, "Soft Tissue and Esthetic Consideration in Implant Therapy" described a pedicle CT grafting technique namely VIP-CT flap. It was introduced as anteriorly based pediculated tissue of palatal submucosa that composed of periosteum and connective tissue. It is preferred for large volume soft tissue augmentation and for simultaneous hard and soft tissue grafting (Sclar 2003).

The procedure involves raising a subepithelial palatal connective tissue periosteal flap and rotating it into the prepared anterior recipient site. It is then positioned beneath the curvilinear recipient flap and rigidly immobilized with sutures(Landi and Sabatucci 2001). The main advantages of this technique are the amount of tissue gain is more and the pedicled blood supply is derived from the connective tissue periosteal plexus within the flap that provides the biological basis for predictable coverage (Rahpeyma, khajeh Ahmadi et al. 2012).

Kim proposed a modified VIP-CT (mVIP-CT) graft in the implant site including papilla preservation flap in the implant site in order to minimizes tissue insult thus reduces postoperative shrinkage, maintains the intact vascularity of donor site even better and achieving optimum results with negligible tissue trauma (**Kim**, **Jang et al. 2012**).

This modification of VIP-CT flap differs from the conventional technique by lacking the releasing incisions at donor site for advancing the pedicle over the recipient site. Instead in this proposed technique, the advancing was done through tunneling procedure. An anteroposterior subperiosteal tunneling was done on the palate near implant site to create a passageway for pedicle graft connecting donor and recipient sites **(Kumar, Gayatri et al. 2015).**

A new soft tissue substitute xenogenic collagen matrix (XCM) is a xenogenicderived absorbable bio-membrane, commonly used as three-dimensional matrix is composed of two layers: a compact layer, which is beneficial to suturing and wound protection, and a porous layer that favours blood clot stabilization, rapid vascularization, and tissue integration(Huang, Liu et al. 2021).

This novel tridimensional xenogenic derived acellular dermal matrix, derived from the porcine dermis composed of natural types I and III collagen without any artificial cross-linking, has been developed for multiple clinical situations (**Papi and Pompa 2018**).

Previous studies have investigated the clinical efficacy of XCM for augmenting keratinized mucosa and reported promising results (Schmitt, Moest et al. 2016).

So, our research aiming to compare between modified VIP-CT graft and xenogenic collagen matrix membrane for soft tissue augmentation around dental implant in esthetic zone.

Aim of the study

-The primary aim of this study is to evaluate the efficacy of mVIP-CT graft technique for soft tissue augmentation around dental implant in esthetic zone.

-The secondary aim is to compare between mVIP-CT graft and xenogenic collagen matrix membrane for soft tissue augmentation around dental implant in esthetic zone.

Patients and methods

Patient selection

This study will be conducted on 20 patients with missing maxillary teeth in esthetic zone seeking its replacement. After approval from the ethical committee, patients will select from the outpatient clinic, Department of Oral medicine, Diagnosis and Periodontology, Faculty of Dentistry, Minia University.

Inclusion criteria

- 1. Selected patients of both sexes are 20-40 years old.
- Patients are systemically healthy based on questionnaire dental modification of Cornell index.
- 3. Good oral health
- 4. The recipient site of the implant is free from any pathological conditions.
- 5. Necessity for soft tissue volume augmentation at the buccal implant site (thin gingival biotype with a narrower zone of keratinized tissue & decrease in papilla height)
- 6. Adequate interocclusal space to accommodate the available restorative components.
- 7. Adequate native/apical bone to achieve primary implant stability.

Exclusion criteria:

- 1. Pregnant female
- 2. Parafunctional habits such as bruxism and clenching Patients suffering from periodontitis.
- 3. Untreated periodontitis and poor oral hygiene
- 4. Patients underwent any prior periodontal surgery in the relevant region for at least 6 months prior to this study
- 5. Smokers.

Ethical regulation

All patients will undergo an immediate implant placement and the complete treatment plan will be explained to all patients including detailed steps, risks, and expected results. Verbal and written informed consent will obtained from all patients before the commencement of the study. All experiments will be examined and approved by the appropriate ethics committee and have therefore been performed in accordance with the ethical standards laid down in the 1964 Declaration of Helsinki and the research ethics committee of the Faculty of Dentistry, Minia University.

Pre surgical phase

- All selected patients will be screened by comprehensive periodontal examination and full periodontal charts will be obtained. A preoperative cone beam computed tomography (CBCT) will be performed for each patient who met the inclusion criteria prior to the surgery to determine bone height and width and decide the implant length and diameter to be placed and to evaluate the underlying bone condition.
- Trans-gingival probing will be done at the mesial line angle 2, 4 and 6 mm apical to the gingival margin. At the same apico-coronal direction three points will be recorded at the mid-buccal and at the distal line angle (Rotenberg and Tatakis 2014)
- 3. The width of keratinized gingiva will be measured using UNC-15 probe and recorded as the distance from the mucogingival junction to the gingival margin.

Randomization

The study will use simple randomization to allocate patients into 2 groups, each group will be included 10 patients.

Then, random allocation will be performed using computer-generated random numbers to determine which group they will be assigned.

• Group 1: Immediate dental implant +Xenogenic bone graft +mVIP-CT graft technique

• Group 2: Immediate dental implant + Xenogenic bone graft+ Xenogenic collagen matrix membrane

Surgical Phase

In group 1" the mVIP-CT group "

- 1. After obtaining adequate local anesthesia (2% lidocaine HCL 1:100000 epinephrine), atraumatic extraction using periotome will done followed by immediate implant placement.
- 2. After ensuring the correct three-dimensional placement of the implant, the jumping distance between the implant and socket will grafted with xenogeic bone graft.
- 3. Soft tissue augmentation will be planned over the implant site. Modified VIP-CT graft will be harvested with modified single incision technique from the palate and the advancement will done through palatal tunneling procedure.
- 4. An anteroposterior subperiosteal tunneling will done on the palate near implant site to create a passageway for pedicle graft connecting donor and recipient sites.
- 5. The posterior end of the tunnel prepared mesial to the single incision on the palate. The passageway of the tunnel prepared will further checked using an instrument.
- 6. Then the flap advanced over the jumping distance through the tunnel into the implant site. The pedicle graft will stabilized using external mattress sutures and the donor site by cross-mattress sutures with 6-0 vicryl suture.

In group 2 " XCM group "

- 1. After obtaining adequate local anesthesia (2%lidocaine HCL 1:100000 epinephrine), atraumatic extraction using periotome will done followed by immediate implant placement.
- 2. After ensuring the correct three-dimensional placement of the implant, the jumping distance between the implant and socket will grafted with xenogeic bone graft.

- 3. The matrix will be rehydrated with sterile saline solution and then trimmed with scissors to fit into the buccal pouch. The matrix, used in one layer with a thickness ranging from 1.2 to 1.7 mm (prior rehydrating).
- 4. The crestal aspect of the split-thickness flap and the underlying CM will be sutured to the palatal flap with interrupted sutures (resorbable, Vicryl 6.0 suture) at the mesial and distal aspects.

Postoperative instructions

- Routine verbal and written postoperative instructions for periodontal surgery will be given to all patients including ice compression on the surgical site during the first 4 h, a liquid and/or soft food diet for 3 days.
- 2. As with all surgical procedures, patients will be informed to contact the therapist if any problems will be developed during postoperative period.
- 3. The postoperative medications prescribed will be (Amoxicillin+ clavulenic acid*625mg for 8 days) * every 8 h or clindamycin 300 g every 8 h for 7 days for patients allergic to penicillin, and (Ibuprofen**600 mg every 12 h for 5 days).
- 4. The patients will be advised to refrain from retracting the lips and cheeks and to avoid brushing or flossing in the grafted area for 6 weeks.
- 5. The sutures remained in situ for 2 weeks.

Clinical assessment:

All patients included in the present study will followed carefully and monitored to motivate the patient for oral hygiene instructions and for maintenance of good oral hygiene.

^{*(} Amoxicillin +clavulenic acid), GlaxoSmithKline, Egypt.

^{**} Brufen ®, Abbott, Egyp

All patients will be examined at baseline (immediately after the implant insertion), 3 and 6 months for the following criteria to evaluate esthetic results around dental implants, include:

- 1. Gingival thickness (GT)
- 2. keratinized tissue width (KTW)
- 3. Pink esthetic score (PES) to evaluate the soft tissue surrounding the crown.
- 4. Buccal bone thickness

Statistical analysis:

-All data will be tabulated and analyzed by statistical method.

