Modified Vascularized Interpositional Periosteal Connective Tissue Graft Versus Xenogeneic Collagen Matrix For soft tissue Augmentation Around Implant in Esthetic Zone (A Comparative Study)

Proposal

Presented By

[name]

25/12/ 2024

Statistical Analysis:

Statistical analysis was performed with IBM® SPSS® (ver. 26. SPSS Inc., IBM Corporation, Armonk, NY, USA). Data explored for normality using Shapiro-Wilk test. Quantitative data were presented by mean and standard deviation. Independent t test was used to compare means between two groups. Paired t test was used to compare between two means before and after treatment within each group. A repeated measure ANOVA is used to compare means in each group across multiple times to see changes to an intervention. A statistically significant level was considered when p value < 0.05.

3. Results:

Twenty patients were recruited in the study, including 12 females and 8 males aged between 20 to 40 years; there were no failed implants or withdrawal of any patients during the follow-up period. Every one of the participants had their planned treatment, and all the implants placed osseointegrated successfully. Data are expressed as mean \pm standard deviation.

3.1 Clinical Parameters:

3.1.1 keratinized tissue thickness: KTT increased from baseline to 3, 6 months in both of groups but more improvement seen in mVIP-CT group than in XCM group at 3 and 6month. No significant differences between the study groups at baseline, but at 3 and 6 month the differences were statistically significant

3.1.2 keratinized tissue width: KTW increased from baseline to 3 ,6 months in both groups but was slightly higher in mVIP-CT group than in XCM group at 6 months with nonsignificant differences between them at baseline and follow up

3.1.3 pink esthetic score: The aesthetic outcome was measured by Pink Esthetic Score (PES), the comparison between both groups revealed a non-significantly higher results in mVIP-CT group than in XCM group

3.2. Radiographic Parameters:

3.2.1 buccal cortex thickness: increased from baseline to 6 month in both of mVIP-CT group and XCM group with no significant differences between the study groups at baseline and follow up period.

KTT	mVIP-CTG group		P value — Baseline	P value Baselin	P value 3	
	Baseline	3 months	6 months	VS	e vs 6 months	months vs 6 months
Mean±SD	1.5±0.53	1.9±0.41	2.8±0.56	0.9	0.001*	0.01*

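### The aims rank stand-alone mVIP-CT efficacy above the randomised comparison with XCM, and with no primary outcome, primary visit or multiplicity rule the 3-month KTT claim is stated too firmly

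*Protocol*

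**What the plan says.** The protocol's Aim of the study section ranks two aims. The first is "The primary aim of this study is to evaluate the efficacy of mVIP-CT graft technique for soft tissue augmentation around dental implant". The second begins "The secondary aim is to compare between mVIP-CT graft and xenogenic collagen matrix membrane". The sentence just before them gives the overall purpose differently: "our research aiming to compare between modified VIP-CT graft and xenogenic collagen matrix membrane". The title also presents the trial as one treatment versus the other.

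The Randomization section defines the arms as "Group 1: Immediate dental implant +Xenogenic bone graft +mVIP-CT graft technique" and "Group 2: Immediate dental implant + Xenogenic bone graft+ Xenogenic collagen matrix membrane". There are 10 patients per arm and no arm without augmentation.

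Clinical assessment says "All patients will be examined at baseline (immediately after the implant insertion), 3 and 6 months for the following criteria" and lists four unranked outcomes: gingival thickness, keratinized tissue width (KTW), pink esthetic score (PES) and buccal bone thickness. The protocol's statistical section is one general sentence.

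The SAP adds "Independent t test was used to compare means between two groups" and "Paired t test was used to compare between two means before and after treatment within each group", a within-group repeated-measures ANOVA, and a 0.05 threshold. It ties no test to an aim, an outcome or a visit. The same document reports results. Section 3.1.1 calls the between-group differences in keratinized tissue thickness (KTT) significant at both 3 and 6 months. Section 3.2.1 reports no significant between-group difference in buccal cortex thickness.

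**The concern.** The ranking and the design point in different directions. Randomisation supports an estimate of mVIP-CT relative to XCM. It supports no estimate of mVIP-CT against no augmentation, because nobody goes without. If the first aim were judged on change within the mVIP-CT arm, the graft could not be separated from the implant, the bone graft and healing. Mean KTT and KTW also rose in the XCM arm (Tables 2 and 5), so a rise from baseline is not specific to mVIP-CT.

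For the comparison itself, nothing says in advance which outcome and visit carry the conclusion. With several tests each at 0.05, the chance of at least one false positive exceeds 0.05, and whether a borderline result counts depends on which tests are taken as one family. The 3-month KTT result is in that position, yet section 3.1.1 gives it the same standing as the 6-month result.

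**Working it through.** **Inputs.** Between-group means, SDs and p-values come from the SAP's between-group tables, n = 10 per arm. Assumptions: KTT is the protocol's gingival thickness; buccal cortex is its buccal bone thickness; the undated PES in Table 10 is post-baseline; tests are two-sided (sidedness is not stated).

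**Step 1: reproduce the stated p-values.** Student t = difference / SE, with SE = sqrt((SD1² + SD2²)/10) and 18 df.

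| Outcome | Difference (mVIP-CT minus XCM) | Recomputed p | Stated p |
|---|---|---|---|
| KTT 3 months | 1.9 − 1.5 = 0.4 | 0.0404 | 0.04 |
| KTT 6 months | 2.8 − 2.0 = 0.8 | 0.0047 | 0.004 |
| KTW 3 months | 1.5 − 1.7 = −0.2 | 0.4055 | 0.4 |
| KTW 6 months | 2.0 − 1.9 = 0.1 | 0.7732 | 0.7 |
| Buccal cortex 6 months | 1.207 − 0.97 = 0.237 | 0.0455 | 0.06 |
| PES | 6.8 − 6.3 = 0.5 | 0.0572 | 0.06 |

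Five of the six agree with the stated value within the rounding of the printed figures. Buccal cortex does not; see step 5.

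**Step 2: familywise error for the six tests.** The outcomes are measured on the same 20 patients, so correlation is expected. Its size is not given. Simulation with equally correlated normal outcomes, n = 10 per arm and 20,000 runs, gave 0.213, 0.167 and 0.111 at correlations of 0.5, 0.7 and 0.9. Independence gives an upper reference of 1 − 0.95⁶ = 0.265. The protocol's schedule implies eight tests (four outcomes at two visits). For eight, the same simulation gave 0.259, 0.196 and 0.119, and independence gives 1 − 0.95⁸ = 0.337.

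**Step 3: Holm on the six stated p-values.** In order: 0.004, 0.04, 0.06, 0.06, 0.4, 0.7.

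- KTT 6 months: 6 × 0.004 = 0.024.
- KTT 3 months: 5 × 0.04 = 0.20.
- Buccal cortex and PES: 4 × 0.06 = 0.24 each.
- KTW 3 and 6 months: 2 × 0.4 = 0.80, carried forward to the last.

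Using the recomputed p-values instead gives 0.028 for KTT at 6 months and 0.202 at 3 months.

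**Step 4: other families.** Over eight tests, with the two unprinted p-values free to lie anywhere from 0 to 1, KTT at 6 months lies between 6 × 0.004 = 0.024 and 8 × 0.004 = 0.032. KTT at 3 months lies between 5 × 0.04 = 0.20 and 7 × 0.04 = 0.28. Within KTT alone the values are 2 × 0.004 = 0.008 and 0.04. Only this last family keeps the 3-month result below 0.05, and neither document defines it.

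**Step 5: buccal cortex at 6 months.** SE = sqrt((0.16² + 0.31²)/10) = 0.110. Student p = 0.0455; Welch p = 0.0504 (13.5 df). The printed values allow means of 1.2065 to 1.2075 and 0.965 to 0.975, and SDs of 0.155 to 0.165 and 0.305 to 0.315. Over those limits Student spans 0.038 to 0.054 and Welch 0.043 to 0.059. A stated 0.06, read as 0.055 to 0.065, is outside the Student range and near the top of the Welch range.

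**Step 6: precision of intervals from the printed figures.** For KTT at 3 months, 0.4 ± 2.101 × 0.181 gives 0.02 to 0.78. Means printed to one decimal let the difference move by up to 0.1 either way. With the SDs also at their rounding limits, the lower limit runs from about −0.09 to 0.12, and p from 0.012 to 0.119. The stated p of 0.04 narrows this, but the printed means are too coarse for a reported interval.

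**The case against.** The strongest reply has four parts.

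- **No document ties the first aim to within-arm tests.** A reader might infer that the primary aim rests on before-after change in one arm. The documents do not say so. The sentence before the aims allows efficacy to be judged against XCM, and the results report between-group comparisons for every outcome with no stand-alone efficacy conclusion. This stands: the harm from the ranking is potential, not shown.
- **Independence is implausible for repeated measures on the same patients.** This also stands. The 26.5% and 33.7% figures are upper references; the correlated range is the better guide, and it rests on assumed correlations.
- **Re-ranking the aims changes wording and no analysis.** Largely true. The practical change is that conclusions rest on the randomised comparison and the 3-month KTT statement is qualified. Declining to choose a primary outcome after seeing the results limits the remedy, but choosing one now would be data-driven.
- **Unprinted comparisons and the buccal cortex p-value are reporting matters.** Agreed; they are kept apart in the fix. A reader might infer selective reporting from the absent 3-month buccal bone result and the single undated PES. The documents do not show whether those assessments were made, so that inference is unsupported.

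**Conclusion.** The point holds, as something the sponsor should correct. The aims place a question that the design cannot isolate above the one it can, and the comparison has no stated primary outcome, primary visit or multiplicity rule. Familywise error over the six printed post-baseline tests is about 11% to 21% at assumed correlations of 0.9 to 0.5.

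The effect on conclusions is limited. A reader might infer that the KTT finding as a whole falls. It does not: the 6-month difference stays below 0.05 under Holm over six tests (0.024) or eight (at most 0.032). Only the 3-month claim depends on the family chosen, at 0.20 over six tests and 0.04 if KTT stands alone.

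Nor does the buccal cortex check show a missed significant result. Student and Welch ranges both straddle 0.05, so the statement in section 3.2.1 is unsettled, and only unrounded data can settle it.

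These conclusions rest on the outcome matching, two-sided testing and the stated p-values.

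**What to change.** 1. Make the randomised mVIP-CT versus XCM comparison the primary aim, record this as a dated post hoc change, and base conclusions on it. The comparison is already in the 2021 title, introduction and allocation, so the re-ranking does not depend on the results. Report within-arm changes as estimates with 95% CIs and no efficacy claim.
2. Do not name a primary outcome now that results are known. Label between-arm results exploratory. Give each difference with a 95% CI computed from patient-level data and the Holm value beside it. In section 3.1.1, say that the 6-month KTT difference stays below 0.05 under Holm over six or eight tests and that the 3-month difference does so only if KTT is its own family.
3. As a separate reporting point, report the scheduled comparisons that are not printed (buccal bone at 3 months, a second PES visit) or say they were not measured, and state the PES visit in Table 10.
4. As a separate point, recompute the 6-month buccal cortex p-value from unrounded data, name the test used, and revise section 3.2.1 if needed.

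**Cost.** Rewording of the aims, the SAP and section 3.1.1, plus reanalysis of existing patient-level data; no new data collection. The downside is that the 3-month KTT claim weakens and the 6-month result is presented as exploratory.

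### Only the mVIP-CT arm has a palatal donor wound, but no scheduled outcome can register donor-site or early transient harm

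*Protocol*

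**What the plan says.** **Aims (Protocol, Aim of the study).** The primary aim is the efficacy of mVIP-CT. The secondary aim is its comparison with the xenogeneic collagen matrix (XCM).

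**Surgery (Protocol, Surgical Phase).** Both arms have extraction, an immediate implant and a xenogeneic bone graft. Group 1 adds a single-incision palatal harvest, a subperiosteal tunnel and a donor site closed with cross-mattress sutures. Group 2 adds a matrix that is rehydrated, trimmed and placed in a buccal pouch, with no harvest step.

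**Outcomes (Protocol, Clinical assessment).** Examinations are at baseline and then "3 and 6 months for the following criteria to evaluate esthetic results around dental implants". The list holds gingival thickness, keratinized tissue width, "Pink esthetic score (PES) to evaluate the soft tissue surrounding the crown", and buccal bone thickness.

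**Postoperative period (Protocol, Postoperative instructions).** Item 2 says that "patients will be informed to contact the therapist if any problems will be developed during postoperative period". Item 5 says: "The sutures remained in situ for 2 weeks". Ibuprofen is a fixed 5-day course.

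**Results (SAP, section 3).** The text says that "there were no failed implants or withdrawal of any patients during the follow-up period", that everyone had the planned treatment, and that all implants osseointegrated. Tables 1 to 10 cover tissue thickness, tissue width, buccal cortex thickness and PES.

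**The concern.** The palatal wound is a main structural difference between the two treatments, and the plan collects no data on it. A comparison of techniques normally weighs gain against burden. Here the SAP reports a 6-month thickness of 2.8 against 2.0 (p = 0.004, between-group KTT table) in favour of the arm with the extra wound, with nothing to set beside it. Analysis cannot recover early wound events or pain that were never recorded. The introduction also describes the modified technique as "achieving optimum results with negligible tissue trauma", so a reader could take the absence of reported harms as confirmation.

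**Working it through.** The plan states no figure on this point, so the check is mainly a comparison of sections. The arithmetic in step 5 is for context.

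**1. What differs between the arms.** Extraction, implant and bone graft are common. Group 1 alone has the palatal incision, the tunnel and the sutured donor site. Group 2 is not free of surgery: it has a buccal pouch and a split-thickness flap sutured to a palatal flap. It has no donor site.

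**2. What is measured.**

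| Scheduled outcome | Site | Could show lasting implant-site loss? | Could show donor-site or transient harm? |
|---|---|---|---|
| Gingival thickness | implant | yes | no |
| Keratinized tissue width | implant | yes | no |
| Pink esthetic score | implant | yes | no |
| Buccal bone thickness | implant | yes | no |

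The count for the last column is 0 of 4. None of the 10 SAP tables reports a harm.

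**3. When it is measured.** Baseline is immediately after implant insertion, and the next examination is at 3 months. The ibuprofen course (5 days) and the suture period (2 weeks) both end well before that. No outcome examination falls in this interval.

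**4. Other routes for harms.** The only stated route for problems is contact initiated by the patient, with no recording, grading or analysis described. Patients are also to be followed and monitored, but the stated purpose is oral hygiene. The SAP's statements on implant failure, withdrawal, treatment completion and osseointegration do not concern the donor site and are not split by arm.

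**5. What a harm record could show with n = 10 per arm** (Protocol, Randomization).

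Exact 95% upper limit after 0 events in 10:
- one-sided: 1 − 0.05^(1/10) = 0.259
- two-sided: 1 − 0.025^(1/10) = 0.308

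The documents give no harm rate, so the rates below are assumptions. The chance of at least one event in an arm is 1 − (1 − p)^10. The last column is the exact power of Fisher's test (two-sided 0.05) against a 0% rate in the other arm.

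| Assumed rate p | Chance of at least 1 event in 10 | Fisher power |
|---|---|---|
| 5% | 40% | not computed |
| 10% | 65% | 0.2% |
| 20% | 89% | 3% |
| 30% | 97% | 15% |
| 50% | not computed | 62% |
| 60% | not computed | 83% |

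For a continuous measure such as a pain score, a normal approximation gives about 80% power only for a difference of 1.25 SD. Ten per arm would probably reveal a common event but could not support a test between arms at modest rates. Any harm table would be descriptive.

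**The case against.** The strongest reply is that the primary aim is efficacy, the SAP claims neither safety nor low trauma, and harm data from 10 patients per arm would be very imprecise. Donor-site events would also have no comparator in group 2. All of this is correct. It limits what the added data could show, but it does not supply the missing side of the secondary comparison.

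Four stronger readings are tempting, and the documents do not support them.

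- **A reader might infer that the outcomes can only favour mVIP-CT or show no difference.** All four can point either way, and no one-sided test is specified. In SAP Table 6 the 3-month mean tissue width is higher with XCM (1.7 against 1.5). The baseline gap was the same (1.6 against 1.4), so this is not a treatment effect, but it shows that the measure can favour either arm.
- **A reader might infer that the trial leaves its own low-trauma hypothesis untested.** The phrase "achieving optimum results with negligible tissue trauma" is background, attributed to a cited study of the modification. The text that follows contrasts that modification with the conventional technique, which has no arm here. The introduction's remark on necrosis concerns large onlay grafts with poor blood supply, not donor-site harm.
- **A reader might infer that wound morbidity is where the arms differ most.** The documents give no figure for it.
- **A reader might infer that the SAP presents its implant-failure sentence as a safety result.** It does not say so.

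One practical objection also stands. A 2-week visit is implied by the suture period but not documented, and the Protocol describes the group 2 sutures as resorbable. The visit should be confirmed before anything is hung on it.

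**Conclusion.** The concern holds as a gap in outcome collection that bears on the secondary aim. No planned measure can register donor-site or early transient harm, although only one arm has a donor site. The trial can therefore say whether mVIP-CT gives more tissue than XCM, but not at what cost in wound morbidity.

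No efficacy estimate or test is affected. The documents give no morbidity figures, so the size of any harm is unknown. With systematic collection, 0 of 10 events would still be compatible with a true rate of up to 26% (one-sided) or 31% (two-sided). With reporting left to the patient and no recording described, no such limit can be stated.

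The conclusion assumes that the surgical steps and assessments are as written, and that no separate adverse-event form exists outside these documents. The change is a cheap improvement.

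**What to change.** **For patients still to be treated.** Use the 2-week suture time point. Confirm that a visit takes place then; if not, use the first postoperative contact. For every patient in both arms, record:
- recipient-site necrosis, dehiscence, bleeding and infection, each yes/no;
- the same four items for the donor site in group 1;
- a 0-10 pain score.

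Tabulate by arm with exact confidence limits, labelled as description only. A count of the ibuprofen doses taken (out of 2 per day × 5 days = 10) is optional, because with a fixed course it partly measures adherence.

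**For patients already treated.** The SAP reports results for all 20 patients, so this part probably matters most. Extract site events from the clinical notes. State that pain and donor-site morbidity were not systematically assessed. Draw no conclusion on safety or low trauma.

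**Cost.** Prospectively, a short form taking a few minutes per patient, with no extra staff or procedure. Retrospectively, a review of 20 records, one table and a limitation statement. The downsides are pain scores that rely on recall, low precision at 10 per arm, and a narrower claim for mVIP-CT.
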